### 9.2 Power analysis

Based on findings in the pilot study (11-CC-0088) [32], calculations indicate that 20 subjects would be needed to detect a significant difference in the main outcome variable of executive functioning with Trail Making Test B for an  $\alpha = 0.05$  and  $\beta=0.05$ . Therefore, 20 subjects in each of the conditions are expected (total 60 subjects). Attrition is approximately one-third for an exercise training protocol, so we predict recruitment of 80 subjects with non-penetrating TBI to have at least 20 subjects in each condition have completed the second assessment visit.

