#### Lead Associate Investigator

[name]	RMD/CC	[name]	[contact]	[contact]
----------------	--------	---------------	--------------	-------------------

Human Research Protections Program Investigator and Staff Training:

For this protocol, the following "Just in time" human subjects protection training courses are required for investigators and staff: None

Total requested accrual: 100 subjects (80 TBI Patients and 20 healthy volunteers)

N = 26 Wait-list control

N = 27 Aerobic Exercise Intervention

N = 27 Rapid-Resistive Exercise Intervention

N = 20 Healthy Volunteer Controls

Project Uses Ionizing Radiation: Medically-indically-i	No [ ated only d only	☐ Yes (attach RSC/RDRC documentation)
IND/IDE Drug/Device/#	🗵 No	$\Box Yes (attach FDA documentation)$
Sponsor:		
Durable Power of Attorney	🗵 No	□ Yes
Multi-institutional Project	□ No	X Yes

Institution#1: Center for Neuroscience and Regenerative Medicine FWA #\_ A00001628\_\_\_\_\_ Date of IRB approval September 15, 2016 (attach IRB documentation)

Institution#2: Department of Veterans Affairs Medical Center, Washington DC FWA # A00002475\_\_\_\_\_ Date of IRB approval January 19, 2018 (attach IRB documentation)

Data and Safety Monitoring Board □ No ⊠ Yes - Monitor

[name]		
University Sports Medicine		
State University of New York at Buff	falo	
[name]		
Office [contact]		
e-mail: [contact]		
Technology Transfer Agreement Agreement type and number Collaboration agreement with DC	□ No CVAMC Expir	☑ Yes – see Appendix 12 ration Date4/19/2022_
Samples are being stored	□ No	🗵 Yes

Flesch-Kincaid reading level of consent form: 10.0

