#### 4.4.8 Randomization

Randomization of subjects will be performed using randomized blocks to keep groups as equal in numbers as possible and to avoid early filling of one of the groups. An independent randomizer that is not affiliated to the protocol will perform the randomization of subjects.

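### Recruiting 80 at one-third attrition leaves an expected 18 completers in each exercise arm, not the 20 or more that section 9.2 states

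*Combined protocol and SAP*

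**What the plan says.** Section 9.2 (Power analysis) sets the requirement at 20 per condition, 60 in all, for 95% power at alpha 0.05 on Trail Making Test B. It then gives the recruitment figure: "Attrition is approximately one-third for an exercise training protocol, so we predict recruitment of 80 subjects". The stated purpose is "to have at least 20 subjects in each condition have completed the second assessment visit".

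The accrual list on the title page splits the 80 TBI subjects: "N = 27 Aerobic Exercise Intervention", "N = 27 Rapid-Resistive Exercise Intervention" and "N = 26 Wait-list control". Section 4.4.8 is consistent with a near-equal split: "Randomization of subjects will be performed using randomized blocks to keep groups as equal in numbers as possible".

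Two other places bear on the count. Section 3.1 caps TBI recruitment at 80, and also says that dropouts will be replaced so that each group has at least 20 completing the second visit. Section 7.3 likewise promises to replace those who withdraw or are withdrawn. Neither section says whether replacements fall inside the 80.

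**The concern.** Section 9.2 links three numbers (20 completers per condition, attrition of about one-third, 80 recruits) and the title page supplies a fourth, the 27/27/26 split. The four do not agree. Adding one-third to a target is not the same as allowing for the loss of one-third: 20 raised by a third is about 27, but 27 reduced by a third is 18.

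The power statement rests on 20 completers per condition. Section 9.1 restricts the analyses to subjects who complete the protocol and are not withdrawn, so the completer count is the analysed sample size. If it is overstated, so is the planned power for any comparison that depends on a single exercise arm. That includes the separate analysis of each exercise condition, from which section 2 expects a significant change in the primary outcome in the aerobic group only.

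**Working it through.** **Inputs.** Completers wanted: 20 per condition, 60 in total (9.2). Attrition: about 1/3 (9.2). Recruits: 80 (9.2, 3.1, title page). Split: 27 aerobic (AET), 27 rapid-resistive (RET), 26 wait-list (title page).

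**Reproducing the plan's figure.** Adding a third to the target gives 60 x (1 + 1/3) = 80, and per arm 20 x 4/3 = 26.7, or 27 rounded up. This matches both the total and the exercise-arm sizes. Section 9.2 does not show the step, so this is the likely source and not a documented one.

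**Dividing by retention.** 20 / (1 - 1/3) = 30 per arm, or 3 x 30 = 90 if all three arms lose a third.

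**Expected completers from the planned split.**

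| Arm | Recruited | Calculation | Expected completers |
|---|---|---|---|
| AET | 27 | 27 x 2/3 | 18 |
| RET | 27 | 27 x 2/3 | 18 |
| Wait-list, same rate | 26 | 26 x 2/3 | 17.3 |
| Wait-list, no loss | 26 | 26 x 1 | 26 |

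The total is 53.3 if the wait-list loses a third and 62 if it loses nobody. The exercise arms expect 18 each in both cases.

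**Attrition the plan can absorb.** One exercise arm: 1 - 20/27 = 25.9%. Wait-list: 1 - 20/26 = 23.1%. Overall: 1 - 60/80 = 25.0%.

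**Range around one-third.** Expected completers per exercise arm are 27 x 0.70 = 18.9 at 30% attrition and 27 x 0.65 = 17.6 at 35%.

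**Chance of at least 20 of 27 completing.** This takes losses as independent (binomial) and assumes no replacement. With retention 2/3 it is 27.5% for one exercise arm and 0.275 x 0.275 = 7.6% for both. At 30% attrition the one-arm figure is 41%, and at 28% it is 50%.

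**Power.** Section 9.2 gives neither the test nor an effect size. As an assumption, the effect is set so that 20 per arm gives exactly 95% power at two-sided alpha 0.05. That means a standardised effect of 0.850 for a paired t-test and 1.170 for an independent t-test.

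| Comparison | Completers | Power |
|---|---|---|
| Paired, one arm | 18 | 92.5% |
| Paired, one arm | 17 | 90.8% |
| Independent | 18 v 18 | 92.6% |
| Independent | 18 v 17 | 91.9% |
| Independent, wait-list fully retained | 18 v 26 | 96.1% |
| Independent, exercise arms combined | 36 v 17 | 97.4% |
| Independent, combined, wait-list fully retained | 36 v 26 | 99.4% |

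A three-group F test on change, over three patterns of means, gives 91.4% to 92.2% at 18/18/17 and 94.1% to 97.1% at 18/18/26.

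**The case against.** **Replacement.** This is the strongest reply. Sections 3.1 and 7.3 promise to replace dropouts, and 3.1 ties replacement to the same target of 20 per group, so 20 could be read as a commitment and not a forecast. But 9.2 derives the 20 from recruiting 80, 3.1 makes 80 the maximum, and the title page requests accrual of 80. If replacements count within the 80, they add nobody. If they do not, the cap and the accrual request are wrong. The documents do not settle which, so the ambiguity is real, but it does not make the figures in 9.2 agree.

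**The rate may not apply to the wait-list.** Section 9.2 gives it for exercise training, and wait-list subjects do not train before the second visit. That could lift the total to 62, but the claim is made for each condition and the exercise arms still expect 18. A total of 80 does work with 20 + 30 + 30 and no wait-list loss, but that is not the documented split.

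**The word approximately, and the period covered.** If one-third describes the whole six months, the loss by the second visit could be smaller. This caveat stands in principle. However, 9.2 uses the rate to justify second-visit completers, and anything above 26% leaves an exercise arm short. The binomial chances do move noticeably with the rate and are best read as a range.

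**Later wait-list training data.** Section 9.1 includes data from immediately before and after exercise for all subjects. If the wait-list's later training is pooled, with a third lost in each period, each regimen has about 18 + (17.3 / 2) x 2/3 = 24, and paired power is about 98%. That lessens the practical harm. Those subjects start training only after the second visit, so they cannot count toward the number in 9.2.

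**Conclusion.** The concern holds. On the plan's own attrition rate and allocation, each exercise arm expects 18 completers at the second visit, two short of the stated minimum. The wait-list expects about 17 if it loses subjects at the same rate. The conclusion for the exercise arms needs only the one-third rate, the 27 per arm and a cap of 80 that includes replacements. It fails only if replacements may exceed 80 or attrition by the second visit is about 26% or less.

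The consequence is modest. Under the assumed effect, power falls from 95% to about 91% to 93% for single-arm and pairwise comparisons at 17 to 18 per arm. It stays above 95% for an exercise arm against a fully retained wait-list and for the combined exercise arms against the wait-list. These power values are illustrative, because the plan names no test or effect size. The completer figure itself is wrong as written.

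**What to change.** In section 9.2, do one of the following:

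- Keep one-third attrition. State 18 expected completers per exercise arm and a wait-list figure with its assumed rate, and quote power at those numbers for a named comparison.
- State that 80 assumes about 25% attrition, and justify that rate. The split then expects 27 x 0.75 = 20.25 in each exercise arm and 26 x 0.75 = 19.5 in the wait-list, so the wait-list needs a rate of 23.1% or less to reach 20.

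In section 3.1, consistently with 7.3 and the title page, say whether replacements count within the 80.

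The cost is one or two sentences in 9.2 and a clause in 3.1. Under the first option the stated completer number, and the power for some comparisons, become slightly less favourable. Correcting the text does not require enrolling more subjects.

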# **10. Human Subjects Protection**

### **10.1 Subject selection**

Subject demographics will be dependent upon the clinical population affected with TBI. Since the majority of TBI occur in men, it is likely that there will be a higher percentage of males in our cohort. However, no preference or exclusion will be granted according to gender or ethnic/racial background, and efforts will be made to recruit under-represented minorities and women.

# 10.2 Justification for exclusion of children

Individuals younger than 18 years of age will not be included in the protocol because reference ranges for normative aerobic capacity and aerobic fitness have not been established for these age ranges. The objectives of this project do not include establishing these normative reference ranges. This lack of information could introduce critical levels of bias into the interpretation and cause the interpretation of our results to be misleading. Thus the exercise responses and adaptations in children and adolescents with TBI should be studied in separate and specific protocols.

### 10.3 Justification for exclusion of other vulnerable population

### 10.3.1 Justification for exclusion of older adults

Individuals 80 years and older will not be included in the protocol as reference ranges for exercise, motor and balance tests for these individuals are not available or well established.

#### 10.3.2 Justification for exclusion of pregnant women

While women will be included in this study, pregnant women will be excluded. This is because of the unknown risk of MRI to an unborn fetus, and the effects of pregnancy on aerobic capacity and the risk that may be associated with beginning a new exercise program while pregnant. Subjects will not be able to participate if the pregnancy test is positive. Subjects that become pregnant during study participation will be administratively withdrawn from the study.

# **10.3.3** Justification for exclusion of mentally ill and those unable to consent themselves

Mentally ill subjects and individuals who cannot give consent themselves will not be included in this study as the research procedures require subjects to follow specific instructions (e.g. hypercapnia challenge in the MRI, neurocognitive measures, exercise and balance testing) and in some cases, provide reliable feedback related to their safety (e.g., indicating when they have approached their limit of tolerance during an exercise test).

#### 10.3.4 Justification for exclusion of non-English speaking subjects

Non-English speakers will be excluded because the neuropsychological assessment instruments we are using are not validated or normed in other languages. Furthermore, many of the tests we are performing would require a native speaking psychometrist to administer theses test, who is not available.

### **10.4 Safeguards for vulnerable populations**

Prior to any MRI scans, urine pregnancy tests will be performed on women of child bearing potential. Monthly pregnancy tests will also be performed in those undergoing the exercise intervention.

### **10.5 Qualifications of investigators**

The Principal Investigator has verified that all individuals working on this protocol required to take HRPP training under OHSRP Policy 201 (Education Program) have completed all required training.

# 11. Anticipated Benefit

### 11.1 Direct benefits

TBI subjects in this protocol have the potential to receive direct benefit from participating in this research. TBI subjects may directly benefit from aerobic exercise training, where improvements in cardiorespiratory fitness enables individuals to accomplish a given amount of activity or work at a lower percentage of maximum capacity and with less fatigue. TBI subjects may also directly benefit from rapid-resistive exercise, with increased strength, flexibility, movement speed and balance. Exercise participation has been shown to be beneficial in the reduction of all-cause mortality and morbidity in some subsets of the population and is recommended for all who are physically able to participate. Healthy volunteers are not expected to receive any direct benefits from participation in this study.

# 12. Classification of risk

This protocol is classified as a greater than minimal risk study. The risks are reasonable in relation to anticipated benefits.

# 13. Consent documents and process

### 13.1 Designation of those obtaining consent

Study investigators designated as able to obtain consent, will obtain informed consent. All study investigators obtaining informed consent have completed the NIMH HSPU "Elements of Successful Informed Consent" training.

# **13.2** Consent procedures

All participants will receive a verbal explanation in terms suited to their comprehension of the purposes, procedures and potential risks of the study and of their rights as research participants. Participants will have the opportunity to review the written consent form carefully and ask questions regarding this study prior to signing.

# 13.3 Consent documents

There is one consent form for the individuals with TBI that contain all the required elements for participating in this study. There is a separate consent form for healthy individuals.

# 14. Data and Safety monitoring

# 14.1 Data and safety monitor

Data and safety will be monitored by the Principal Investigator, [name] at least once a year. In addition, a data and safety monitor, [name], will review all adverse events at least every 6 months (see section on Data and Safety Monitoring Plan).

# 14.2 Data and safety monitoring plan

Data and safety monitoring for this protocol is an ongoing process. The PI will meet weekly with the study team to discuss the protocol progress and any relevant activities or occurrences. However, research staff have been instructed to report any issues related to protocol safety and data as soon as possible after occurrence or when they first became aware of it to the PI. The PI is then responsible for evaluating these, proposing and implementing corrective action as needed, and reporting these to the IRB in a timely manner.

As the principle investigator, [name] will be contacted after every serious adverse event that is related to the protocol and notified of all deaths. These will also be reported to the NIH and USUHS IRB's with the continuing review.

[name] is a physician with cardiology experience and specific expertise in rehabilitation and management of persons with concussion/brain injury. He has been enlisted to conduct an independent data and safety monitoring review no less than every 6 months for this study. [name] is board certified in Internal Medicine with a subspecialty in Sports Medicine, and is a Professor of Clinical Orthopaedics and Rehabilitation Sciences at the State University of New York at Buffalo. He is also the Medical Director of the Concussion Management Clinic in the Jacobs School of Medicine and Biomedical Sciences, and Division I Team Physician at the University at Buffalo. He will be apprised of all adverse events and will have access to study related data to make his assessment and review as deemed necessary.

# 14.3 Criteria for stopping the study or suspending enrollment or procedures

The PI, data and safety monitor ([name]), and IRBs will assess the measures taken by the study team in response to safety issues that caused the study to be stopped or suspended. Revised safety measures taken by the study team will be in a written report submitted to the IRBs of record. Only when these entities agree in writing that the problems have been satisfactorily addressed can the protocol may be re-activated.

Annually there will be a continuing review of this study at the NIH and USUHS IRBs.

# **15. Quality Assurance**

### **15.1 Quality Assurance monitor**

This study will be monitored for quality assurance through the NIH Clinical Center's Quality Assurance Program.

# 15.2 Quality Assurance Plan

Accrual and safety data will be monitored by the principal investigator, who will provide oversight to the conduct of this study. The PI will continuously evaluate implementation of the protocol for any unusual or unpredicted complications that occur and will review the data for accuracy and completeness.

The NIH Clinical Center's Quality Assurance Program will conduct study monitoring at least annually. Monitoring visits will include a review of patient consent documents, primary outcome and safety laboratory results and diagnostic test results will be monitored for accuracy, correct dating, and agreement between case report forms and source documents. All regulatory reports, reviews and amendments, adverse events and problem reports related to study, along with investigator credentials, training records, and the delegation of responsibility log will also be reviewed during monitoring visits. Any major findings will be summarized in writing and reported to the study PI who will be responsible for submitting the monitoring report to the IRB.

All study staff will maintain current training in good clinical practice and protection of human subjects, and will complete other protocol- and role-specific training, as needed.

# **16. NIH Reporting Requirements**

# 16.1 Adverse Event Definitions

Please refer to definitions provided in Policy 801: Reporting Research Events.

### **16.2 Expedited Reporting**

Please refer to the reporting requirements in Policy 801: Reporting Research Events.

The data and safety monitor ([name]) will also be notified of all adverse events at least every 6 months.

It is anticipated that participants in this study may fail to complete the entire list of assessments or procedures, such as questionnaires or neuropsychological tests. Omissions such as these will be considered expected events and not protocol deviations provided they are infrequent, not the primary outcome, not related to determination of the exercise training range and do not include data needed to assess safety for a procedure. Cumulative proportions of these missed events in the study population will be presented to the IRB at the time of Continuing Review. In addition, the rate of omissions will be monitored by the Investigators. If an individual misses more than 15% of the required assessments/procedures or if more than 15% of the participants miss completion of the same assessment or procedure, it will be considered a deviation and reported according to Policy 801.

# 16.3 IRB Requirements for PI Reporting at Continuing Review

Please refer to the reporting requirements in Policy 801: Reporting Research Events.

### **16.4 Clinical Director Reporting**

Problems expeditiously reported to the IRB in iRIS will also be reported to the Clinical Director. A separate submission is not necessary as reports in iRIS will be available to the Clinical Director.

# **17.** Alternatives to participation

Subjects do not receive any treatment in this study or forego any treatment in order to participate in this study. The alternative, therefore, is not to participate.

# **18.** Privacy

All research activities will be conducted in as private a setting as possible.

# **19. Confidentiality**

Confidentiality of patient files will be maintained at all times. Samples and data will be de-identified, using codes that we assign. Data will be kept in password-protected computers. Samples will be kept in locked freezers in locked rooms. Paper records and case report forms will be maintained in locked rooms, or in computer files protected by computer passwords. Only study investigators will have access to the samples and data. In the presentation of research results, no information will be given that may reveal the identity of the research subjects. The consent form will discuss patient confidentiality protection.

De-identified results from clinical trials will be posted on clinicaltrials.gov

Confidentiality of the patient records will be protected to the extent possible under existing regulations and laws but cannot be guaranteed. Complete confidentiality cannot be promised, especially to military personnel, because information bearing on their health may be required to be reported to appropriate medical or command authorities. Members of CNRM, Uniformed Services University, Henry M Jackson Foundation, US Department of Defense (DoD), and NIH, may have access to the study data for auditing purposes.

Each study participant will be assigned a study number that will be used on study data collection forms and samples. The link between the study number and participants' identity will be kept on a password-protected computer. Only study researchers and members of the IRB will have access to identified information. Data transmitted to the Data Coordinating Center will be coded. Investigators at the clinical site where consent was obtained will have access to identifying information for the patients enrolled in the study at their site. Only coded de-identified information will be shared with persons outside of the enrolling site, except for audits.

NIH will assign a Global Unique Identifier (GUID) to all data submitted to the CNRM Repository. The purpose of the GUID is to allow data on the same subject, from multiple protocols and from different institutions, to be identified as coming from a single individual and to be combined in the repository. PII will be entered on a local server and a one-way encryption using a keyed-hash algorithm will be used to assign the GUID. CNRM will not receive PII. The one-way encryption assures that the GUID cannot be used to back-generate PII. Data that were delinked may then be sent to other non-CNRM Biorepositories.

Blood will be processed and frozen according to CNRM Biospecimen Repository guidelines for confidentiality. Samples will be assigned a unique identifier at time of blood draw. The key for the re-identification of samples will be maintained on a master list in the PI's office and accessible only to his designees. Some information will be on a password-secured server in one of the Investigator's offices on the NIH campus.

